### 7.3 Rationale for Correlative Studies

To compare the pharmacokinetics (PK) of evolocumab in treated patients, peripheral blood samples will be taken to compare serum concentrations of evolocumab to intratumoral concentrations. These are further detailed in Section 10.

Tumor-infiltrating lymphocytes (TILs) from tumor or liquid obtained from the surgical field will be dissociated into a single cell suspension or fragmented and TILs expanded as one batch following the TILs pre-rapid expansion protocol (preREP). The ability to successfully and reliably expand preREP TILs from lung cancer and glioblastoma samples has been previously demonstrated in Pro00106078. TILs, in general, display a profound degree of exhaustion. Therefore, cells will be stained for expression of surface and nuclear markers of exhaustion (PD-1, Lag3, TIM3) and activation (CD137) and differential levels assessed by flow cytometry. CD137 is upregulated on T cells during early activation immediately following interaction with tumor antigen in the Tumor Microenvironment (TME). We will explore the potential to select and expand the non-exhausted CD137+ subset and examine their anti-tumor efficacy in samples from patients treated with or without evolocumab. Autologous CD137+ TIL cell product will be co-cultured with disassociated CFSE labeled neurospheres for 24 and 48 hours. Cytotoxicity determined by flow cytometry of CFSE+ tumor cells will be compared to no TIL exposure. Patient-derived neurospheres will be generated *in vitro* based on established protocols .

### 7.4 Definition of Evaluable Subjects, On Study, and End of Study

Once a patient has their baseline PK collection (both arms) and receives one dose of Evolocumab (treatment arm only), that patient will be considered “on study.” Different definitions for “on study,” “on treatment,” “off treatment,” and “off study” may be required in the electronic research record. Rationale for taking a patient off protocol treatment will be documented.

Any patient who receives one dose of Evolocumab will be included in safety analyses. Once all data has been collected, analyzed, and completely evaluated on all subjects, as defined in the statistical analysis plan, and subjects have completed follow up, expired, withdrawn, or been lost to follow up, the study will be ended.

### 7.5 Early Study Termination

This study can be terminated at any time for any reason by the PI or Sponsor- Investigator. If this occurs, all subjects on study should be notified as soon as possible. Additional procedures and/or follow up should occur in accordance with Section 10.7, which describes procedures and process for prematurely withdrawn patients.

## 8 STUDY DRUG

### 8.1 Names, Classification, and Mechanism of Action

Evolocumab (Repatha®) is a PCSK9 inhibitor and binds to a pro-protein involved in the regulation of LDL receptors on liver cells; receptor numbers are increased, which results in increased uptake of LDL-cholesterol from the blood. Evolocumab is currently indicated :

- In adults with established cardiovascular disease to reduce the risk of myocardial infarction, stroke, and coronary revascularization
- As an adjunct to diet, alone or combined with other low-density lipoprotein cholesterol (LDL-C)-lowering therapies, in adults with primary hyperlipidemia, including heterozygous familial hypercholesterolemia (HeFH), reducing LDL-C

- As an adjunct to other LDL-C-lowering therapies in patients with homozygous familial hypercholesterolemia (HoFH), to reduce LDL-C

## 8.2 Packaging and Labeling

Please refer to the current evolocumab (REPATHA®) labeling on [Drugs@FDA](#).  
<https://www.accessdata.fda.gov/scripts/cder/daf/index.cfm?event=overview.process&ApplNo=125522>

## 8.3 Supply, Receipt, and Storage

Evolocumab is available commercially from Amgen and is a clear to opalescent, colorless to pale yellow solution supplied as follows:

*Table 3. Formulations of Evolocumab*

140 mg/mL single-dose prefilled syringe	1 pack	NDC 72511-750-01 NDC 55513-750-01
140 mg/mL single-dose prefilled SureClick® autoinjector	1 pack	NDC 55513-760-01
140 mg/mL single-dose prefilled SureClick® autoinjector	2 pack	NDC 72511-760-02 NDC 55513-760-02
140 mg/mL single-dose prefilled SureClick® autoinjector	3 pack	NDC 55513-760-03
420 mg/3.5 mL single-dose Pushtronex® system (on-body infusor with prefilled cartridge) Formulation to be used in this study	1 pack	NDC 72511-770-01 NDC 55513-770-01

### Per the package insert:

The needle cover of the glass single-dose prefilled syringe and the single-dose prefilled autoinjector contain dry natural rubber (a derivative of latex). The single-dose on-body infusor with prefilled cartridge is not made with natural rubber latex.

Store refrigerated at 2°C to 8°C (36°F to 46°F) in the original carton to protect from light. Do not freeze. Do not shake.

For convenience, evolocumab may be kept at room temperature at 68°F to 77°F (20°C to 25°C) in the original carton for 30 days. If not used within the 30 days, discard evolocumab.

## 8.4 Dispensing and Preparation

The commercial agent will be purchased from the pharmacy storeroom and managed by ICS. Evolocumab is a sterile, preservative-free, clear to opalescent, colorless to pale yellow solution for subcutaneous use. Each single-dose Pushtronex® system (on-body infusor with prefilled cartridge) delivers a 3.5 mL solution containing 420 mg Evolocumab, acetate (4.2 mg), polysorbate 80 (0.35 mg), proline (89 mg) in Water for Injection, USP. Sodium hydroxide may be used to adjust to a pH of 5.0 .

## 8.5 Compliance and Accountability

Evolocumab will be delivered from Duke Pharmacy directly to the clinic under the supervision of the research nurse, or his/her designee. Evolocumab will be administered according to the approved labeling. The patient's name, Study ID, DOB, and Duke history number will be double verified prior to subcutaneous injection as is standard Duke procedure.

## 8.6 Disposal and Destruction

All injection equipment will be disposed of according to standard Duke procedures. Unused medication will be returned to Duke pharmacy, if possible, or disposed of as per standard handling of clinical medicines.

## 9 SUBJECT ELIGIBILITY

### 9.1 Inclusion Criteria

#### Both arms:

1. Adult patients  $\geq 18$  years old
2. Newly diagnosed or recurrent glioma or glioblastoma (GBM) (if recurrent, prior pathology report indicating glioma)
3. A clinical indication for gross macroscopic resection, debulking of the glioma, or biopsy, with sufficient tumor size that can allow collection of specimens for the required analyses.

#### Treatment arm only:

4. Adequate hematologic function within 14 days prior to starting evolocumab defined as follows:
  - a. Hemoglobin  $\geq 10$  g/dL (*Note: the use of transfusion or other intervention to achieve Hgb  $\geq 10.0$  g/dL is acceptable*)
  - b. White Blood Cells  $\geq 1.5 \times 10^9$ /L
  - c. Absolute Neutrophil Count (ANC)  $\geq 1.0 \times 10^9$ /L
  - d. Platelets  $\geq 100 \times 10^9$ /L or  $\geq 50,000$  for patients who received TMZ within the past year
5. Adequate renal function within 14 days prior to starting evolocumab defined as calculated creatinine clearance (CrCL) of  $\geq 30$  mL/min/1.73m^2 by the Cockcroft-Gault formula
6. Adequate hepatic function within 14 days prior to starting evolocumab defined as follows:
  - a. Total bilirubin  $\geq 1.5 \times$  institutional upper limit of normal (ULN) (*Note: Patients with known Gilbert disease without other clinically significant liver abnormalities are not excluded.*)
  - b. AST(SGOT) and ALT(SGPT)  $\geq 1.5 \times$  ULN
7. Negative serum pregnancy test (in females of childbearing potential) within 48 hours of starting evolocumab.

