### 9.2 Exclusion Criteria

#### Treatment arm only:

1. Any patient with a history of a serious hypersensitivity reaction to evolocumab or any of the excipients in evolocumab
2. Patients with severe hepatic impairment outside of the range defined in the inclusion criteria within 7 days of starting evolocumab.
3. History or evidence of central nervous system bleeding as defined by stroke or intraocular bleed (including embolic stroke) not associated with any antitumor surgery within 6 months before enrollment
4. Infection requiring intravenous antibiotics that was completed  $< 1$  week of study enrollment (day 1) with the exemption of prophylactic antibiotics for long line insertion or biopsy
5. Females of reproductive potential and males who are unwilling to practice an acceptable method(s) of effective birth control while on study through 1 month (2 half-lives) after receiving the last dose of study drug.

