## 10.1 Screening Examination

The initial screening examination will take place at a Duke PRTBTC clinic visit. The patient will sign either the main Evolocumab treatment consent form or the control consent form for this study and then undergo peripheral blood draw (prior to administration of evolocumab for those in the treatment arm). All patients with resectable tumors or tumors amenable to biopsy will complete screening and confirm their eligibility per the inclusion/exclusion criteria in Section 9. Screening tests in the treatment arm will consist of a physical and neurological exam, CBC with differential, CMP, lipid panel, and Beta HCG quantitative (if applicable).

 Consent can be obtained within 30 days before starting evolocumab.

 Patients in the treatment arm will be followed for ongoing serious adverse events and new onset serious adverse events for 30 days following evolocumab injection.

 Within 48 hours of the first evolocumab injection, if applicable. Will only be repeated on Day 1 if screening pregnancy test is outside of the 48-hour window.

 Tube type to be determined by the Proteomics Core.

 Estimated > 50-100 mg from surgical resection or de-bulking procedure; Estimated > 20 mg from a minimum of 2 cores from biopsy

Once the patient is confirmed eligible, patients in the treatment arm will then receive Evolocumab via subcutaneous injection 4-14 days prior to surgical procedure. If the first evolocumab injection does not start within two weeks of the screening visit, the CBC with differential, CMP, lipid panel, and clinic visit (physical/neuro exam) will need to be repeated.

Patients who consent to participate as a control will not undergo any screening tests or procedures.

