### **13.8 Sample Size Calculation**

The sample size selected was chosen for practical considerations in the setting of a phase 0 study, to allow descriptive analysis of the changes of the biologic endpoints in the evolocumab treated (cases) and untreated patients (controls). This may provide important biologic insights into the secondary and exploratory endpoints.

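### Hepatic inclusion criterion 6 is printed with its inequality signs reversed, so it admits only treatment-arm candidates with raised liver tests

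*Combined protocol and SAP*

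**What the plan says.** Section 9.1 lists the treatment-arm laboratory criteria. Criterion 6 opens with "Adequate hepatic function within 14 days prior to starting evolocumab defined as follows" and has two parts:

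- 6a, total bilirubin: "\geq 1.5 \times$ institutional upper limit of normal (ULN"). A note adds: "Patients with known Gilbert disease without other clinically significant liver abnormalities are not excluded".
- 6b, transaminases: "AST(SGOT) and ALT(SGPT) $\geq 1.5 \times$ ULN".

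In both parts the printed sign is greater than or equal to.

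Section 9.2, exclusion 2 (also treatment arm only) bars "Patients with severe hepatic impairment outside of the range defined in the inclusion criteria within 7 days of starting evolocumab". It gives no limit of its own and refers back to criterion 6.

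Section 10.1 makes these criteria operative: candidates complete screening and "confirm their eligibility per the inclusion/exclusion criteria in Section 9". No other section restates or corrects the hepatic limits. Controls have no hepatic criterion and no screening tests.

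**The concern.** Bilirubin, AST and ALT are abnormal when high, so a criterion for adequate function should cap them. As printed, 6a and 6b set floors and leave the top open. Criterion 6 is the hepatic check before study drug is given ahead of surgery or biopsy, and the only other hepatic safeguard, exclusion 2, takes its range from it.

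Two outcomes are possible, and neither gives a compliant trial of the evidently intended population:

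- **The text is followed.** Only patients with all three tests raised can be dosed, which is a patient-safety problem. It would also set a treated arm selected for liver dysfunction against controls with no hepatic criterion, although Section 7.1 says controls are recruited on similar criteria and the planned comparisons include lipid metabolism.
- **The text is ignored.** Patients with normal tests are dosed, and each one is an eligibility deviation. Section 12.1 has the monitoring team review whether enrolled patients are eligible, and Section 10.8.1 lists protocol deviation among the reasons for withdrawal by the PI.

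**Working it through.** No sample-size or power figure is involved. Section 13.8 states only that "The sample size selected was chosen for practical considerations in the setting of a phase 0 study", so there is no planned number to reproduce. The check is logical.

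**Step 1. Apply the printed rule.** A candidate meets criterion 6 if bilirubin ≥ 1.5 × ULN (6a) and both AST and ALT ≥ 1.5 × ULN (6b). Example candidates, in multiples of ULN:

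| Bilirubin | AST and ALT | 6a | 6b | Criterion 6 as printed |
|---|---|---|---|---|
| 1.0 or below | 1.0 or below | fails | fails | not met |
| 1.4 | 1.4 | fails | fails | not met |
| 2 | normal | passes | fails | not met |
| 1.5 | 1.5 | passes | passes | met |
| 10 | 10 | passes | passes | met |

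Every candidate with normal results is turned away. No degree of elevation is turned away, because no upper limit exists.

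**Step 2. Set the printed rule beside the surrounding text.**

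- *Label.* The criterion is introduced as a test of adequate function. The printed condition describes raised liver tests.
- *Gilbert note.* An exemption for Gilbert disease has a purpose only if raised bilirubin would otherwise exclude. Under the printed sign raised bilirubin is required, so the note does nothing. The patient it describes, with no other significant liver abnormality, would ordinarily have AST and ALT below 1.5 × ULN and fail 6b.
- *Exclusion 2.* It places severe impairment outside the inclusion range. The printed range runs from 1.5 × ULN upwards without end, so the only values outside it are those below 1.5 × ULN. Worsening impairment never leaves the range.

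**Step 3. Reverse the signs and repeat.** With 6a and 6b as upper limits, the label fits, the Gilbert note becomes a real exemption, and exclusion 2 has an upper end to refer to. All three conflicts disappear together. Under the printed signs none is resolved.

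**Step 4. Compare the neighbouring criteria.** Criterion 4 uses ≥ for hemoglobin, white cells, neutrophils and platelets, and criterion 5 uses it for creatinine clearance. Low values are the abnormal ones there, so ≥ is sensible. The hemoglobin note ("the use of transfusion or other intervention to achieve Hgb" the threshold) confirms that reading. Only in criterion 6 does the sign run against the meaning.

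**The case against.** **A misread character.** The point turns on one symbol, and converting a PDF to text can misread it. Every non-strict inequality in the document text is ≥ and no ≤ appears, so the sensible signs in criteria 4 and 5 do not show that a ≤ would have been read correctly. This stands as a reason to look at the source page. It does not defeat the point: the sign appears separately in 6a and 6b, strict less-than signs come through correctly elsewhere, and nothing indicates a misreading.

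**Nobody would apply it literally.** The label, the note and exclusion 2 make the intention plain, the study runs at one centre with at most 10 treated patients and a single dose, and the document does not show that anyone was screened by the literal text. This lowers the likelihood of harm. It does not cure the rule, because Section 10.1 sends staff to Section 9 and monitoring works from the printed criteria.

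**Exclusion 2 still names severe impairment.** A clinician would probably not read it as permitting a patient at 10 × ULN. That is fair as a matter of judgement, but the exclusion has no usable bound, because its range comes from the defective criterion.

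**It is a typographical slip with no statistical effect.** No planned figure changes, and the analysis sets in Section 13.1 do not depend on eligibility. The slip nevertheless sits in an operative rule on who may be dosed.

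**Conclusion.** The concern holds. As printed, criterion 6 excludes every treatment-arm candidate with bilirubin, AST or ALT below 1.5 × ULN, admits those with all three at or above that level without limit, and leaves exclusion 2 with no working upper bound. It touches all treatment-arm screening, for an arm of at most 10, and does not affect controls. It changes no planned estimate, test or sample size.

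The consequence of the printed text follows directly. That the signs are reversed is an inference from the label, the Gilbert note and exclusion 2, which all point the same way. The conclusion assumes that the source PDF shows the same signs. This must be fixed because it is the hepatic check before dosing.

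**What to change.** 1. Confirm the two signs on the source PDF page. If they stand as printed, amend 6a and 6b from ≥ to ≤ so that both are upper limits. The direction comes from the protocol's own label, note and exclusion 2. The 1.5 multiple is the sponsor's to confirm, and no other value is proposed here.
2. In the same amendment, reconcile exclusion 2 with criterion 6 so that the range it refers to has an upper end. Reconcile the look-back windows too: criterion 6 uses 14 days before starting evolocumab and exclusion 2 uses 7. Table 4 and Section 10.1 require the metabolic panel only within 14 days, so results 8 to 14 days old can serve criterion 6 but fall outside the exclusion 2 window.
3. Review the records of every treatment-arm candidate already screened. Establish which reading was applied, and document any resulting deviation or wrongful exclusion.

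The cost is two characters for the signs, a short edit to exclusion 2 and a record check for a small arm. Sections 14.2 and 14.7 require IRB approval of the amendment and say the PRMC should be informed of eligibility changes. The design, the sample size and the budget are unaffected.

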### 9.2 Exclusion Criteria

#### Treatment arm only:

1. Any patient with a history of a serious hypersensitivity reaction to evolocumab or any of the excipients in evolocumab
2. Patients with severe hepatic impairment outside of the range defined in the inclusion criteria within 7 days of starting evolocumab.
3. History or evidence of central nervous system bleeding as defined by stroke or intraocular bleed (including embolic stroke) not associated with any antitumor surgery within 6 months before enrollment
4. Infection requiring intravenous antibiotics that was completed  $< 1$  week of study enrollment (day 1) with the exemption of prophylactic antibiotics for long line insertion or biopsy
5. Females of reproductive potential and males who are unwilling to practice an acceptable method(s) of effective birth control while on study through 1 month (2 half-lives) after receiving the last dose of study drug.

## 10 SCREENING AND ON-STUDY TESTS AND PROCEDURES

Table 4. Schedule of Events for Treatment Arm

Description	Screening (within 14 days of starting evolocumab)	Treatment Period	Active Follow-up Period

	Pre-Evolocumab Screening	Evolocumab Injection	Surgical Procedure	Post-Operative Visit
Day(s)		1	4-14	Typically ~2 weeks following surgery
General Evaluations				
Evolocumab Informed Consent	X 			
Physical Exam	X			X
Neurologic Exam	X			X
Adverse Events			Continuous 	
Laboratory Evaluations				
CBC with differential	X			X
CMP	X			X
Lipid profile	X			
Serum Pregnancy Test, if applicable	X 	X 		
Pharmacokinetic blood draws (5 mL) 		X	X*	
Tumor tissue analysis (estimated >20mg available) 			X	
Treatment				
Evolocumab		X		

\* This blood sample taken at time of surgery or biopsy so that drug level in the blood can be compared to intratumoral concentration.

**Table 4** shows the schedule of events for the treatment arm of this study, including all study-related general evaluations, laboratory evaluations, disease evaluations, and treatments. Of particular importance for this phase 1 study are the tumor sampling and pharmacokinetic blood draws to investigate evolocumab concentration profiles following agent administration. Patients who consent to participate as a control will only be asked to have the following:

- Informed consent on the control consent form
- PK blood draw prior to surgical procedure
- Tumor tissue analysis, if available

## 10.1 Screening Examination

The initial screening examination will take place at a Duke PRTBTC clinic visit. The patient will sign either the main Evolocumab treatment consent form or the control consent form for this study and then undergo peripheral blood draw (prior to administration of evolocumab for those in the treatment arm). All patients with resectable tumors or tumors amenable to biopsy will complete screening and confirm their eligibility per the inclusion/exclusion criteria in Section 9. Screening tests in the treatment arm will consist of a physical and neurological exam, CBC with differential, CMP, lipid panel, and Beta HCG quantitative (if applicable).

 Consent can be obtained within 30 days before starting evolocumab.

 Patients in the treatment arm will be followed for ongoing serious adverse events and new onset serious adverse events for 30 days following evolocumab injection.

 Within 48 hours of the first evolocumab injection, if applicable. Will only be repeated on Day 1 if screening pregnancy test is outside of the 48-hour window.

 Tube type to be determined by the Proteomics Core.

 Estimated > 50-100 mg from surgical resection or de-bulking procedure; Estimated > 20 mg from a minimum of 2 cores from biopsy

Once the patient is confirmed eligible, patients in the treatment arm will then receive Evolocumab via subcutaneous injection 4-14 days prior to surgical procedure. If the first evolocumab injection does not start within two weeks of the screening visit, the CBC with differential, CMP, lipid panel, and clinic visit (physical/neuro exam) will need to be repeated.

Patients who consent to participate as a control will not undergo any screening tests or procedures.

## 10.2 Run-In Period

Not applicable.

## 10.3 Treatment Period

### Day 1:

- Baseline pharmacokinetic (PK\_ blood draw (applies to patients who consent to either arm of the study) (5 mL drawn). For patients in the treatment arm, PK blood draw should occur before Evolocumab injection. For patients in the control arm, this blood draw can occur prior to the scheduled day of the surgical procedure or on the day of the surgical procedure. [Error! Bookmark not defined.](#)

#### Treatment arm only:

- Beta HCG quantitative (if applicable) only if screening pregnancy test is outside of the 48-hour window
- Evolocumab injection
  - Latex-sensitive patients will be cautioned that the needle cover of the glass single-dose prefilled syringe and the single-dose prefilled auto-injector contain dry natural rubber (a derivative of latex) that may cause allergic reactions in individuals' sensitive to latex
  - Evolocumab will be allowed to warm to room temperature for at least 30 minutes for the prefilled auto-injector or syringe and for at least 45 minutes for the single-dose Pushtronex® system (on-body infusor with prefilled cartridge) if evolocumab has been refrigerated.
  - Evolocumab will be administered subcutaneously into areas of the abdomen, thigh, or upper arm that are not tender, bruised, red, or indurated, avoiding injecting into areas with scars or stretch marks.
  - The 420 mg dose of Evolocumab can be administered either:
    - Over 5 minutes by using the single-dose Pushtronex® system (on-body infusor with prefilled cartridge)
    - By giving 3 injections consecutively within 30 minutes using the single-dose prefilled auto-injector or single-dose prefilled syringe.
- Adverse events monitoring

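### Section 10.3 permits auto-injector or syringe dosing although 8.3 designates only the latex-free on-body infusor, and latex-sensitive patients get only a caution (minor inconsistency)

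*Combined protocol and SAP*

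**What the plan says.** Section 8.3 (Table 3) lists the commercial presentations of evolocumab, beginning with the "140 mg/mL single-dose prefilled syringe" and followed by the auto-injector in three pack sizes and the 420 mg/3.5 mL on-body infusor. Only the infusor row carries the note "Formulation to be used in this study". Section 8.4 then gives the composition and volume for the infusor and for no other device.

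The package-insert text reproduced in 8.3 states: "The needle cover of the glass single-dose prefilled syringe and the single-dose prefilled autoinjector contain dry natural rubber (a derivative of latex"). It adds that the infusor is not made with natural rubber latex.

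Section 10.3, Day 1, treatment arm, is the instruction that staff follow when dosing. It opens the choice of device with "The 420 mg dose of Evolocumab can be administered either" and gives two routes. One is the infusor over 5 minutes. The other is "By giving 3 injections consecutively within 30 minutes using the single-dose prefilled auto-injector or single-dose prefilled syringe". The preparation bullet also covers the second route: "Evolocumab will be allowed to warm to room temperature for at least 30 minutes for the prefilled auto-injector or syringe", with 45 minutes for the infusor. On latex, 10.3 says: "Latex-sensitive patients will be cautioned that the needle cover of the glass single-dose prefilled syringe and the single-dose prefilled auto-injector contain dry natural rubber", and goes on to acknowledge that this can provoke an allergic reaction in sensitive people.

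**The concern.** The supply section and the dosing section do not authorise the same set of devices. A nurse who gives three injections from the auto-injector or syringe complies with 10.3 but departs from the designation in 8.3. The protocol does not settle whether that is a deviation.

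The mismatch matters a little more than most wording slips because it touches a hazard that the protocol itself names. The designated device avoids the rubber, while the two extra devices bring it in, and for a latex-sensitive patient the only stated response is a warning. Nothing in 10.3 directs staff to use the infusor for such a patient.

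What is at stake is participant safety in a rare circumstance, and a clean attribution if a reaction did occur. Section 11.1 grades causality against the study drug only. A reaction to the needle cover could therefore be hard to tell from a reaction to evolocumab in a group of at most 10 treated patients.

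**Working it through.** No statistical figure is involved, so the check compares the sections, with two small pieces of arithmetic.

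**Devices by section**

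| Device | 8.3 Table 3 | 8.4 preparation | 10.3 Day 1 | Rubber or latex status (8.3) |
|---|---|---|---|---|
| On-body infusor, 420 mg | Listed, marked for the study | Described | Permitted, over 5 minutes, 45-minute warm-up | Not made with natural rubber latex |
| Auto-injector, 140 mg | Listed, not marked | Not described | Permitted, 3 injections, 30-minute warm-up | Dry natural rubber in needle cover |
| Prefilled syringe, 140 mg | Listed, not marked | Not described | Permitted, 3 injections, 30-minute warm-up | Dry natural rubber in needle cover |

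The study-use note sits in the infusor row and 8.4 agrees with it, so a misread table is an unlikely explanation.

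**Extent of the text mismatch** (not a measure of risk)

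- Presentations in Table 3: 1 syringe + 3 auto-injector packs + 1 infusor = 5. Marked for study use: 1. Unmarked: 5 - 1 = 4.
- Bullets in 10.3 that refer to the unmarked devices: the latex caution, the warm-up time and the three-injection option, which makes 3. With the lead-in to the choice of device, 3 + 1 = 4 items of text need editing.

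**Dose**

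- Three injections: 3 x 140 mg = 420 mg.
- One infusor: 420 mg.
- Difference: 0 mg. Both routes are subcutaneous.

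**Does another section close the gap?**

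- *8.5* requires dosing in line with the approved labeling. The label text reproduced in 8.3 states the rubber content and prohibits no device.
- *8.5* also has the pharmacy deliver the drug to the clinic under research-nurse supervision. This makes use of another device unlikely but does not withdraw the permission in 10.3.
- *9.2*, criterion 1, excludes serious hypersensitivity to evolocumab or its excipients. Latex is not named, and the ingredients listed in 8.4 do not include rubber.
- *10.9.1* collects past medical history at screening. Latex allergy is not mentioned, and no action on device choice follows from it.
- *11.1.1* lists allergic reaction and anaphylaxis as events of special interest. That provides for detecting a reaction, not for preventing one.

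None of these bars the rubber-containing devices for a latex-sensitive patient.

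**Risk.** An expected number of reactions would need the proportion of latex-sensitive patients, the probability that a non-designated device is used, and a reaction rate for that device. The documents give none of the three, so no figure is calculated.

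**The case against.** The strongest reply is that the sections can be followed together. Table 3 catalogues what is sold and then makes the study's choice. Section 10.3 is permissive and puts the infusor first, so it can be read as general label-style instructions subject to the choice in 8.3. A site that uses the infusor satisfies 8.3, 8.4 and 10.3 at once, and nobody faces two contradictory commands. Harm would need a latex-sensitive patient among at most 10, a departure from the designated device, and staff going ahead despite the caution. Dosing is supervised, adverse events are monitored from Day 1, and allergic reactions are already of special interest. The full label is not reproduced in the protocol, so the documents do not show that a caution falls short of what the label asks.

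Much of this stands. Harm is unlikely, the issue is one of wording and not of device choice, and whether a caution meets the label cannot be judged from the excerpt. It is also fair that equal dose is not proof of equal exposure, since the documents do not compare drug levels by device.

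The permission itself remains. Section 10.3 is where staff look on the day, it authorises devices that 8.3 does not designate, and the safeguards cited either detect a reaction afterwards or make the situation less likely. The case for a change does not depend on what the label requires, because the protocol has already chosen a device that avoids the exposure.

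**Conclusion.** The point holds as a minor inconsistency. Section 10.3 permits two devices that 8.3 does not designate, and those two carry the rubber hazard that the protocol describes. A latex-sensitive patient is protected only by a caution and by the likelihood that the infusor will be used in practice.

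Its reach is small. It concerns at most 10 treated patients (section 3.3), and the probability of harm is low but cannot be quantified from the documents. No endpoint or analysis is affected. That last statement rests on the nominal dose and the subcutaneous route being the same for every permitted option, and it assumes that exposure does not differ materially by device. Using the infusor throughout would make the issue moot.

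**What to change.** Limit 10.3 to the designated device with four edits:

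1. Delete the three-injection option.
2. Delete the latex caution, which is no longer needed.
3. Shorten the warm-up bullet to the infusor's 45 minutes.
4. Replace the lead-in that offers a choice with a single instruction to give 420 mg over 5 minutes with the on-body infusor.

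If the sponsor wants a fallback for supply problems, list the auto-injector and syringe in 8.3 as fallback devices, keep their instructions in 10.3, and replace the caution with a rule that they are not to be used in latex-sensitive patients.

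The cost is a few lines of text, which can go into the next IRB-approved amendment under 14.7. No urgent action is needed. The first route gives up a little supply flexibility; the second keeps it for everyone who is not latex-sensitive.
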